# 9.3 **Populations for Analyses**

The following data sets are defined for analysis:

Screen Failures (SFs): comprises all subjects who consent to participate in the clinical trial but are not subsequently randomly assigned to treatment in the trial.

Intent-to-Treat (ITT): comprises all randomized subjects

Full Analysis Set (FAS): comprises all randomized subjects who receive at least 1 dose of IMP

Modified ITT (mITT) Set: comprises all randomized subjects who receive at least 1 dose of IMP and have at least 1 entry in the seizure diary.

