An additional key secondary endpoint is the 50% responder rate, defined as the percentage of subjects with at least a 50% reduction in the Maintenance Phase focal onset seizure frequency relative to the Baseline Period. This key secondary endpoint will be analyzed for the mITT population using a logistic regression model with effects for treatment. Odds ratios representing the odds of being a responder compared with placebo will be constructed for each CVL-865 treatment group. Subjects with missing or incomplete seizure information will be treated as non-responders for this analysis.

Continuous endpoints with repeated post-baseline assessments (CGI-S, CGI-I, PGIC) will be analyzed for the mITT population using a Mixed Model for Repeated Measures (MMRM). This estimand will include available post-baseline response data that occur before discontinuation of treatment. The baseline score (if applicable) will be included as the covariate, and treatment group (CVL-865 7.5 mg, CVL-865 25 mg, or placebo), visit, and the interaction between treatment group and visit will be included as fixed factors in the MMRM. The difference between each CVL-865 level versus placebo at each visit will be estimated based on the LSMeans from the MMRM. Changes from baseline in QOLIE-31 Domain and Overall Scores and HUI Utility Function scores will be analyzed using an analysis of covariance model (ANCOVA) with the baseline score and treatment group included in the model as fixed effects. The difference between each CVL-865 level versus placebo will be estimated based on the LSMeans from the ANCOVA model.

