1.1. Study Overview

This is a double-blind, parallel-group, placebo-controlled trial with subjects randomized to 1 of the following 3 arms in a 1:1:1 ratio:

- CVL-865 25 mg BID maintenance
- CVL-865 7.5 mg BID maintenance
- Placebo

This maximum duration is to be approximately 25 weeks, consisting of the following:

- 8-week Screening/Baseline Period
- 10- or 13-week Treatment Period, including an initial 2-week Titration Phase, an 8-week Maintenance Phase, and a 3-week Taper Phase (only for subjects not continuing treatment in the open-label extension trial). The tablets (including the number of tablets given) will be the same between the placebo and both CVL-865 dose arms during the Titration, Maintenance, and Taper Phases to maintain the blind
- 4-week Follow-up Period (only for subjects not continuing treatment in the openlabel extension trial)

Subjects are to continue on their current AEDs at the same dosages throughout the Screening/Baseline Period. If a subject has a vagus nerve stimulator (VNS), a deep brain stimulator (DBS), or a responsive neurostimulator (RNS), the settings must remain stable throughout the Screening/Baseline Period.

During this Screening/Baseline Period, subjects will be required to complete electronic seizure diaries (eDiary) and record all seizures in the eDiary for each day and days free of seizures. The presence or absence of all seizure types experienced by each subject will be recorded daily in the eDiary.

Subjects who satisfy all inclusion/exclusion criteria and thus are eligible for the trial will be randomized to 1 of 3 treatment arms at Visit 1 (Day 1). The daily dosing schedule will start at Day 1 with a 2-week Titration Phase during which time the subject's dose will be increased in a blinded fashion up the randomized dose level (CVL-865 25 mg BID, CVL-865 7.5 mg BID, or placebo). In the high-dose group, CVL-865 will be administered as

during the Titration Phase, and then 25 mg BID during the 8-week Maintenance Phase. In the low-dose group, CVL-865 will be administered as

during the Titration Phase, and then

7.5 mg BID during the 8-week Maintenance Phase.

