4.2. Analysis Periods

The start and end dates of each analysis period (following the study design) are used for the classification of efficacy data. The exact start and end of each of these periods is described for calculation purposes in Section 4.3. Seizure frequency and average daily dose for each analysis period will be calculated based on Table 3.

Table 3:	Definition of Analysis Periods for Seizure Frequency and Average Daily Dose
	Data

Analysis Period	Duration	Start Date	End Date
Baseline Period	~8 Weeks	The greater of: Study Day, -56 or Informed consent	Study Day, -1
Titration Phase	~2 Weeks	Study Day, 1	The lesser of: Day 15 (Visit 2) minus 1 or *Early termination (minus 1) or End of Treatment
Maintenance Phase	~8 Weeks	Day 15 (Visit 2)	The lesser of: **Day 71 (Visit 4) minus 1 or *Early termination (minus 1) or End of Treatment
Taper Phase	~3 Weeks	Day 71 (Visit 4) or *Early termination	End of Treatment

* If a subject experiences early termination from the study and continues to Taper Phase, end dates will be bound by early termination minus 1 while the start of Taper Phase will begin on the date of early termination. ** For subjects continues to Taper Phase from Maintenance Phase

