5.2. Populations for Analyses

The analysis populations are defined Table 10.

Population	Description	Analysis
All Screened Subjects	All Screened Subjects includes all subjects who signed the informed consent form.	Disposition
ITT	All randomized subjects	Disposition, Demographic and Baseline Characteristics
FAS	All randomized subjects who receive at least 1 dose of IMP. This will be the safety analysis set.	Safety analysis
mITT	All randomized subjects who receive at least 1 dose of IMP and have both baseline seizure frequency recorded in the eDiary with entry compliance $\geq 20\%$ and at least 1 post baseline entry in the seizure diary during maintenance phase.	Primary analysis set for efficacy
PK Analysis Set	All randomized subjects who receive at least 1 dose of IMP and have at least 1 measurable CVL-865 concentration	PK analysis

Table 10:Populations for Analysis

Abbreviations: FAS = full analysis set, IMP = investigational medicinal product, ITT = intent-to-treat, mITT = modified intent-to-treat, PK = pharmacokinetic.

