5.8.4.3. Impact of Discontinuation Potentially Related to Treatment

The seizure frequency data of subjects who discontinue of from the trial on or before Week 6 (Visit 3) for the following reasons are potentially missing not at random (MNAR).

- AE with AEHLGT eq 'Seizures (incl subtypes)'
- WITHDRAWAL BY SUBJECT
- LACK OF EFFICACY
- LOST TO FOLLOW-UP

In this assessment, the subjects with MNAR (to be identified and documented in Section 9.5 before database lock) will be imputed by jump to reference approach.

Specifically, the missing values in each of the active group will be imputed using the multiple imputation procedure described above except that the missing observations in CVL-865 group are not constructed from the observed data in the respective groups, but rather from the observed data in the placebo group. Any missing data from the placebo group is imputed using the observed data from the placebo group. The data will be log transformed using convention log(X+1) and back transformed to conform to the multivariate normality distribution. The

proc mi data = mcmc1 (where=(((y = . or y0=.) and trt ne 'Placebo') or (trt='Placebo' and (y0 ne. and y ne .)))) seed = SEED1 nimpute = 10 minimum =0 minmaxiter = 1000 out= Out1X; mcmc chain = multiple displayinit initial=em(itprint); var y0 y; run;

Where y represents $\ln(7 \text{ day average seizure frequency over maintenance period + 1})$, y0 is $\ln(7 \text{ day average seizure frequency over the baseline period+1})$, and SEED1 is a random number. Each of these datasets will be analyzed using the same ANCOVA model through SAS PROC MIXED as described in Section 5.8.3. The results of the analyses of the datasets will be combined using PROC MIANALYZE to produce an inferential result.

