5.10.2. Main Analytical Approach for Second Key Secondary Endpoint

The second key secondary endpoint, 50% responder rate, will be analyzed for the mITT population using a logistic regression model with effects for treatment and baseline seizure frequency. The binary outcome will be defined as having at least a 50% reduction in the maintenance phase relative to the baseline period or not having a 50% reduction. Odd ratios will be constructed for each CVL-865 treatment dose group compared with placebo and will be summarized with 90% confidence intervals. Subjects with greater than 80% missing seizure diary entries will be treated as non-responders for this analysis. Should a logistic regression model fail to converge, paired Fisher's exact tests will be used instead.

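### The SAP's mITT removes subjects who stop during titration from the 50% responder analysis, whereas the protocol keeps them as non-responders

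*SAP*

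**What the plan says.** **Protocol.** Section 9.3 defines the mITT as the set that "comprises all randomized subjects who receive at least 1 dose of IMP and have at least 1 entry in the seizure diary". It sets no condition on when the entry is made, so a baseline or titration entry is enough. Section 9.4.1 analyses the 50% responder rate in that set and adds: "Subjects with missing or incomplete seizure information will be treated as non-responders for this analysis".

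**SAP.** Table 10 (5.2) keeps the name mITT but requires baseline diary compliance of at least 20% and "at least 1 post baseline entry in the seizure diary during maintenance phase". Table 3 (4.2) starts Maintenance at Day 15 (Visit 2). Its footnote says that, for a subject who terminates early and goes on to taper, "end dates will be bound by early termination minus 1 while the start of Taper Phase will begin on the date of early termination". Section 5.10.2 analyses the responder rate in this mITT with its own missing-data rule: "Subjects with greater than 80% missing seizure diary entries will be treated as non-responders for this analysis".

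**Sensitivity analyses.** Section 5.8.4.2 bases its multiple imputation on the mITT. Section 5.8.4.3 (jump to reference) covers stops up to Week 6 for four listed reasons and reuses the imputation procedure of 5.8.4.2. Section 5.10.3 carries both over to the responder endpoint.

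SAP section 6 does not record the narrower mITT as a change from the protocol.

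**The concern.** Take a subject dosed on Day 1 who stops on Day 10. Under the protocol this subject is in the mITT, has no Maintenance seizure information, and is a non-responder. Under the SAP the subject has no Maintenance Phase and so cannot make the qualifying entry. Diary days after the stop fall in taper or later and do not restore eligibility. The SAP's non-responder rule operates only inside its mITT, so it never reaches this subject.

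Reaching Maintenance is a post-randomisation event that treatment can influence. Conditioning on it removes subjects who can only have been non-responders, so the rate rises in any arm with titration stops. If one arm loses more subjects this way, the responder difference and odds ratio shift in that arm's favour. The baseline-compliance condition does not raise this problem, because it is settled before treatment starts.

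**Working it through.** **The plan's own figures.** Neither document gives a figure for titration stops. The nearest is the sample-size allowance: 50 per arm with 20% dropout leaves 50 × 0.80 = 40 evaluable, as stated. At 40 per arm, a difference of 20, SD 34 and two-sided alpha 0.10, power is 83.2% by the t-test, consistent with the stated minimum of 80%. This point does not depend on that figure. It shows only that the allowance is 10 dropouts per arm over the whole trial.

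**Formula.** Let n be the randomised and dosed subjects in an arm, s the titration stops and x the responders. No titration stop can be among the x.

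- Protocol rule: x / n.
- SAP rule: x / (n − s).
- Ratio of the two: n / (n − s), which exceeds 1 whenever s > 0.

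**Inputs.** n = 50 per arm is from the documents. The values of x and s are assumed. Subjects who stop later, in Maintenance, are handled alike in both calculations, so only the denominator moves. Odds ratios are crude, whereas the SAP model also adjusts for baseline seizure frequency.

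**Results with x = 18 (active) and 10 (placebo).** The protocol rule gives 18/50 = 36.0% vs 10/50 = 20.0%, difference 16.0 points, odds ratio (18/32)/(10/40) = 2.25, whatever the stops. The SAP rule gives:

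| Stops, active vs placebo | Active | Placebo | Difference (points) | Odds ratio |
|---|---|---|---|---|
| 2 vs 1 | 18/48 = 37.5% | 10/49 = 20.4% | 17.1 | (18/30)/(10/39) = 2.34 |
| 5 vs 1 | 18/45 = 40.0% | 10/49 = 20.4% | 19.6 | (18/27)/(10/39) = 2.60 |
| 8 vs 1 | 18/42 = 42.9% | 10/49 = 20.4% | 22.4 | (18/24)/(10/39) = 2.93 |
| 3 vs 3 | 18/47 = 38.3% | 10/47 = 21.3% | 17.0 | (18/29)/(10/37) = 2.30 |
| 1 vs 5 | 18/49 = 36.7% | 10/45 = 22.2% | 14.5 | (18/31)/(10/35) = 2.03 |

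The last two rows matter. Equal stops move the difference by 1 point, and more stops on placebo move it the other way.

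**Against the 0.10 level (unadjusted pooled z-test).** With 18 vs 10 responders and 5 vs 1 stops, p is 0.075 under the protocol rule and 0.038 under the SAP rule, so the conclusion is the same. With 16 vs 10 responders, p is 0.17 under the protocol rule. Under the SAP rule it is 0.10 with 5 vs 1 stops and 0.063 with 8 vs 1. A changed conclusion is possible but needs a marked imbalance.

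**RRatio and log change.** Both need a Maintenance seizure rate. A titration stop has none under either document, so that subject adds nothing to either document's main ANCOVA.

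**The case against.** **The protocol delegates this.** Section 9.4 leaves the SAP to describe the analysis populations and the handling of missing data, and the SAP states its mITT openly in 5.2 and 5.8.5. That stands as authority to refine the set. It does not remove the effect of selecting on a post-randomisation event, and here it replaces a rule that the protocol states for a key secondary endpoint.

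**The estimand is hypothetical.** SAP 5.10.1 assumes that data missing after a stop follow the subject's observed trajectory. A titration stop has no Maintenance trajectory to follow, and the population definition removes the subject before the strategy can apply.

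**Much would be visible anyway.** SAP 5.6 and 5.7 tabulate the analysis sets, discontinuation reasons and days in each phase by arm. This stands: a reader could largely see who is excluded. Those tables do not show the responder comparison with these subjects counted.

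**Imbalance is assumed.** This also stands. The documents give no titration stop rates, the titration doses are not visible, and the full assigned doses begin on Day 15, so stops at full dose fall in Maintenance and inside the SAP's mITT. A reader might infer that the exclusions are known to favour the active arms. The documents do not support that.

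**Jump to reference may already cover these stops.** A reader might infer that it cannot, because its code picks active-arm subjects with a missing baseline or Maintenance value and mITT members appear to have both. That is too absolute. Section 5.8.4.2 sets a period to missing when over half its entries are missing, subjects listed as missing not at random may have values set to missing, and the Week 6 window includes titration by its terms. The text is unclear rather than shown to exclude them. Even on the generous reading, its only adverse-event reason is seizure events.

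**Conclusion.** The mismatch is clear on the text: the protocol counts a titration stop as a 50% non-responder, and the SAP drops that subject from the analysis. Any arm with titration stops shows a higher responder rate than under the protocol rule, by a factor of n/(n − s). The effect on the between-arm difference depends on the imbalance in stops, which the documents do not allow anyone to estimate. In the assumed cases above it runs from a 1.5-point reduction to a 6.4-point increase on a difference of 16.0 points.

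Two wider readings should be resisted. A reader might infer that the primary RRatio result and the log-change result depart from the protocol in the same way. They do not, since neither document's main ANCOVA can use a subject without a Maintenance rate. A reader might also infer that the protocol counts titration stops as not seizure-free. Its rule names only the 50% responder endpoint.

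The point concerns one key secondary endpoint in a trial that the SAP (5.4) calls exploratory. It should still be corrected, because the remedy is small and the rule is already in the protocol.

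**What to change.** 1. **Responder endpoint (SAP 5.2, 5.10).** Analyse it in all randomised, dosed subjects with a usable baseline diary (the existing 20% condition can serve), without requiring a Maintenance entry. Count those who stop before Day 15 as non-responders, as the protocol does. Apply the same denominator to seizure freedom as a supportive analysis, noting that this extends the protocol rule.
2. **Jump to reference (SAP 5.8.4.3).** State that it is run on that same set, with the Maintenance rate of titration stops set to missing so that it is imputed.

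Leave the primary ANCOVA on the mITT as it is.

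The cost is SAP wording and a few extra tables, with no new data. The downside is that the reported responder difference may be less favourable.

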5.3. Statistical Hypotheses

The primary efficacy hypotheses and the key secondary hypotheses will be tested with 2-sided tests of superiority comparing each active CVL 865 dose (CVL1-25 mg BID, CVL2-7.5 mg BID) to placebo at individual test α level of 0.1.

Primary Endpoint	Active CVL 865 dose vs Placebo	
Response ratio (RRatio)		
Key Secondary Endpoints		
Change from baseline in focal onset seizure frequency per week over the Maintenance Phase	 H₀₁: µ_{placebo} = r_{CVL1} vs H₁₁: µ_{placebo} ≠ r_{CVL1} H₀₂: µ_{placebo} = r_{CVL2} vs H₁₂: µ_{placebo} ≠ r_{CVL2} 	
Percent of subjects with at least a 50% reduction in the Maintenance Phase focal onset seizure frequency rate relative to the Baseline Period		

5.4. Multiplicity Adjustment

As the study is of exploratory nature, multiplicity adjustment is not planned.

5.5. Strata and Covariates

No stratification was implemented in randomization. The baseline value of each efficacy variable will be included as a covariate in the efficacy analyses.

5.6. Subject Disposition, Demographic and Baseline Characteristics

Subject disposition will be based on the ITT population. The number of subjects who completed the study, discontinued from the study, reason for early discontinuation of the study at any point, and discontinuation relationship to COVID-19 also will be presented by treatment group. Additionally, the number of days on study will be summarized for all treated subjects.

The number of subjects who are screened, screen failed, reason for screen failures and reason related to COVID-19 will also be summarized.

Number of subjects in each analysis population set will be summarized.

Demographic data including age, sex, race, ethnicity, height (at screening), weight (at screening), and BMI (at screening) will be summarized by treatment group using descriptive statistics within the ITT population.

5.6.1. Medical History

Medical history and ongoing medical conditions will be listed and summarized by MedDRA system organ class (SOC) and preferred term (PT). The start date and end date (or ongoing if applicable) will be included in the listing as collected.

5.6.2. History of Epilepsy

The number and percentage of subjects who received epilepsy surgery and the type of surgeries will be summarized.

Epileptic seizure profile is based on the historical seizure types reported by the subject on the Seizure History form. The number and percentage of subjects experiencing each seizure type at any time in the past will be summarized.

The number and percentage of subjects with each category of focus localization will be summarized. Subjects may be counted in more than one category of focal localization. The average number of seizures for each category of focus localization will be summarized.

The date of diagnosis of epilepsy is collected on Seizure History eCRF. If the date of diagnosis date is missing, the date will be imputed as the earliest start date of any Anti-Epileptic Drug taken. The duration of epilepsy will be derived as the years between informed consent date and diagnosis date as reported on the Seizure History eCRF. The duration of epilepsy and age at epilepsy diagnosis will be summarized descriptively.

The background AEDs and history of RNS/VNS procedures at study entry will also be summarized.

5.7. Exposure to Treatment

The number of days on study drug, reasons for premature discontinuation of IMP, treatment compliance, days in each phase (Titration, Maintenance, and Taper), average dose in each phase, will be summarized by treatment group for the FAS Population.

5.7.1. eDiary compliance

Primary and secondary, and other efficacy variables are based on diary-collected seizure frequencies, and as such, diary compliance will be evaluated along with treatment compliance. Subjects are instructed to complete their diary entries at least once a day during the study. A diary day will be considered missing for compliance if a seizure diary record is missing for that day. Diary compliance will be evaluated during the Baseline Period, during the entire Treatment Period, and during the Maintenance Period.

Diary compliance will be calculated as 100 times the number of diary days (days with diary completed) during the period and dividing this quantity by the expected number of diary days that should have been completed during this period of time. Compliance is only computed for actual time of participation in the study up to the end of the Treatment Period. Only data prior to and on the date of last dose of study medication will be included in the compliance calculation. If a subject didn't enter an analysis period, the diary compliance for the analysis period will not be calculated.

Diary compliance data will be listed by treatment then subject.

Cerevel

5.8. Primary Efficacy Analysis

5.8.1. Derivation of Primary Efficacy Endpoint

The primary efficacy endpoint is the response ratio (RRatio) over the Maintenance Phase:

$$RRatio = \frac{T-B}{T+B} \times 100$$

where T =focal onset seizure frequency rate per week in the Maintenance Phase and

B = focal onset seizure frequency rate per week in the Baseline Period

It ranges between -100 and 100 where negative values will indicate reduction in seizure rate and positive values indicate increase in seizure rate during treatment.

5.8.2. Primary Estimand

The key research question for the primary endpoint will be addressed with an estimand based on the following attributes:

- 1. Treatments: treatments as randomized regardless of the actual treatment received.
- 2. Target study population of interest: subjects in the modified intent-to-treat (mITT) population.
- 3. Endpoint (variable) of interest: RRatio over the Maintenance Phase.
- 4. Population level summary of interest: difference between CVL-865 treated and placebo subjects in RRatio over the Maintenance Phase.
- 5. Strategy for Intercurrent events (ICEs): a hypothetical strategy will be used to address intercurrent events (ICEs) of potential death, and treatment discontinuations. The data after treatment discontinuations will typically be missing or be treated as missing even if collected. Under the hypothetical strategy, these missing values as the result of ICEs of discontinuation will be assumed to follow the observed trajectory of the subject and thus the endpoint will include only eDiary based response data that occur before discontinuation of treatment. It should be noted that the use of protocol defined rescue medication will not be considered as an ICE.

